## Dose of study drug -

Low dose 100 mg/kg/day Medium dose 200 mg/kg/day High dose 300 mg/kg/day

[figure not shown]
**When to start study drug -** Study drug will be started when infant has been off of TPN for at least 3 days so that IV arginine in TPN does not interfere.

**Sample collection** - 1 mL of blood will be collected from each subject at 2 time points: before starting citrulline (Day 0) and then after completing 1 week enteral L-citrulline supplementation (Day 7). Discarded blood sample from routine blood draw will be used.

It is standard of care for all preterm infants to get weekly blood draws on Tuesdays for hemoglobin monitoring. We will use discarded blood sample from the Tuesday after being on full feeds (no TPN) and start enteral L-citrulline supplementation on the first Tuesday (Day 1) after off TPN for at least 3 days. After 1 week, supplementation will be discontinued (last dose Monday PM) and discarded blood sample from Tuesday (Day 7) will be used to analyze plasma levels or L-citrulline and L-arginine. Immediately after blood collection, blood will be centrifuged at 4-degree C to extract serum. Serum will be divided into aliquots of 100 microliter & stored at -80-degree C for future use.

1 mL of urine will be collected before starting (Day 0) and then daily thereafter till the last day of L-citrulline supplementation (Day 7). Urine will be collected by placing cotton balls in diapers at around noon  $\pm$  2 hours (in between the 2 doses of study drug).

All sample collection will be part of routine/standard care of the infant and no extra blood draws/invasive procedures will be needed.

Sample collected - (time points)

- \*Discarded blood (for arginine, citrulline & ADMA)
- ^Urine daily for urinary arginine, citrulline, nitrites and nitrates

**\*Enteral L-citrulline** –low, medium or high dose divided into 2 doses via gavage feeding tube i.e. 10% L-citrulline twice daily.

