**Measurements:** 

**Serum L-citrulline & L-arginine measurement** - We will measure amino acids (AA) in serum using an HPLC-MS approach. A cocktail of stable-isotope enriched AA will be added to serum samples & AA will be extracted using a solid-phase cartridge. Extracted AA will be separated by HPLC (C-18 Colum) eluted with a methanol ammonium formate gradient. AA will be injected directly into a QTRAP 6500 instrument tuned for low mass analyses. AA will be detected using characteristic fragmentation ions. Concentrations of AA in the original sample will be determined by co-paring peak areas to those of the stable isotope-enriched internal standards. For this initial study, we will measure citrulline & arginine.

**Urinary nitrates and nitrite measurement (metabolites of NO)** - Urinary nitrite, nitrate and creatinine will be measured by GC-MS following conversion to the pentafluorobenzyl derivatives.

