### 9.0 Statistical Considerations

Study design: Single-center Pilot dose-ranging study

Study population: Premature infants admitted to the Neonatal intensive care unit at UTMB, Galveston.

Rationale: L-citrulline has been shown to increase NO production in neonatal pigs. The use of L-citrulline in premature infants may help increase NO and prevent pulmonary hypertension that develops due to chronic lung disease. Even though L-citrulline has been used safely in infants and children for urea cycle disorders, its dosage, efficacy and safety have not been evaluated in premature infants. Therefore, a pilot dose-ranging study is essential.

There will be 3 study groups in this Phase I trial:

Group 1 (Low dose): 100 mg/kg/day of L-citrulline Group 2 (Medium dose): 200 mg/kg/day of L-citrulline Group 3 (High dose): 300 mg/kg/day of L-citrulline

Sample size: A sample size of 14 at each group (low, median, and high dose) for efficacy endpoint will reach a power of 0.80 to

detect an effect size of 0.5 based on one-way analysis of variance (ANOVA) with a 0.05 significance level. The sample size calculation was based on the following expected mean  $\pm$  SD citrulline concentrations in plasma according to the study from Schwedhelm et al:

Low dose group:  $19 \pm 4 \ \mu mol/L$ Medium dose group:  $21 \pm 4 \ \mu mol/L$ High dose group:  $45 \pm 5 \ \mu mol/L$ 

Primary outcome:

1. Increase in plasma L-citrulline levels and increased NO production (measured indirectly via urinary breakdown products)

Secondary outcomes:

- 1. To determine safety of enteral L-citrulline supplementation in premature infants.
- 2. To determine the dose of enteral L-citrulline needed to increase plasma level of citrulline > 37 mol/L.

Data will be collected from electronic medical records. Measurements will be recorded in a password protected computer on an excel sheet.

A Data Safety Monitor Board (DSMB) as mentioned in section 7.0 will be reviewing safety data every 4 months.

The data will be analyzed at the end of data collection for all subjects who meet the inclusion criteria. SPSS version 24 will be used for data analysis. SAS procedures, linear models, repeated measures analysis of variance (ANOVA) & logistic modeling for receiver operator curve generation (significance p<0.05) will be used. The UTMB Clinical trials studio will be involved to assist in statistics.

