# Procedure for accounting for any missing, unused and spurious data:

In this pilot study, subjects with missing data on important predictors (lack of blood sample for serum arginine/citrulline levels) will be excluded from analyses.

Selection of subjects to be included in the analyses:

We will follow an intention-to-treat approach in the analyses. The primary variables (plasma arginine, citrulline levels and urinary nitrite, nitrate levels) are continuous data

and the one-way ANOVA will be used to analyze differences amongst the 3 treatment groups from day 0 and day 7. Paired T-test will be used to evaluate differences pre-and post-treatment in individual subjects. The data gathered from daily urinary nitrite and nitrate measurements will be represented in line graphs to represent the trend.

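### Daily urinary nitrite/nitrate, part of the primary outcome, has no longitudinal analysis tied to it, and the NO variable itself is not defined

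*Combined protocol and SAP*

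**What the plan says.** All references are to the combined protocol and SAP.

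- **Role of the outcome.** Section 9.0 pairs plasma L-citrulline with "increased NO production (measured indirectly via urinary breakdown products" as the primary outcome. Later in that section: "The primary variables (plasma arginine, citrulline levels and urinary nitrite, nitrate levels) are continuous data".
- **Sampling.** Section 5.0, under sample collection: "1 mL of urine will be collected before starting (Day 0) and then daily thereafter till the last day of L-citrulline supplementation (Day 7". The samples are spot urines from cotton balls in the diaper.
- **Assay.** Section 5.0, under measurements: "Urinary nitrite, nitrate and creatinine will be measured by GC-MS following conversion to the pentafluorobenzyl derivatives". Creatinine is mentioned nowhere else.
- **Assigned methods.** Section 9.0, under selection of subjects: "the one-way ANOVA will be used to analyze differences amongst the 3 treatment groups from day 0 and day 7". A paired t-test covers pre- and post-treatment differences. For the daily values: "The data gathered from daily urinary nitrite and nitrate measurements will be represented in line graphs to represent the trend".
- **General list of methods.** Earlier in section 9.0: "SAS procedures, linear models, repeated measures analysis of variance (ANOVA" and logistic modelling are to be used. None of these is linked to a variable, a set of days or a contrast.

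**The concern.** Only the daily urine has an explicit schedule of more than two study measurements, and it serves a primary outcome. Yet where the plan names this variable, it assigns tests at two days and a display for the days between. A single spot urine is a noisy measure, and a dose effect on NO could be missed although the repeated samples that would show it are already collected and assayed.

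The variable is also left open. It could be nitrite, nitrate or their sum, and it could be a concentration or a ratio to creatinine. With that choice and the choice of longitudinal method both unstated, either could be made after the data are seen.

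**Working it through.** **1. The plan's own figure.** Three groups of 14, effect size f = 0.5, alpha 0.05. One-way ANOVA noncentrality = f² × N = 0.25 × 42 = 10.5 on 2 and 39 degrees of freedom, giving power 0.803. The stated 0.80 reproduces. Section 9.0 bases it on expected plasma citrulline. No mean, SD, effect size or power is given for urinary NO, so 0.80 is not used as a starting point below. Only relative information is computed.

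**2. Samples outside the assigned tests.** With the day labels at face value there are 8 samples per infant, so 42 × 8 = 336. Days 1 to 6 give 42 × 6 = 252, and 252/336 = 75%. Section 5.0 calls the first Tuesday of dosing Day 1 and the Tuesday a week later Day 7, so the count could be off by one.

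**3. Information, constant effect.** Assumptions: equal variance each day (set to 1), the same correlation ρ between any two days (compound symmetry), and ρ from 0.3 to 0.9. The comparator is an ANOVA of the day 7 minus day 0 change, one reading of the assigned test.

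- Two-day change: variance A = 2(1 − ρ)
- Mean of days 1–7 adjusted for Day 0: B = (1 + 6ρ)/7 − ρ²
- Day 7 adjusted for Day 0: C = 1 − ρ²

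| ρ | A | B | A/B | C | C/B |
|---|---|---|---|---|---|
| 0.3 | 1.40 | 0.310 | 4.5 | 0.91 | 2.9 |
| 0.5 | 1.00 | 0.321 | 3.1 | 0.75 | 2.3 |
| 0.7 | 0.60 | 0.253 | 2.4 | 0.51 | 2.0 |
| 0.9 | 0.20 | 0.104 | 1.9 | 0.19 | 1.8 |

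A/B is the gain over the two-day change. C/B shows that most of it comes from the extra days, beyond the Day 0 adjustment.

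**4. Information, effect growing linearly to day 7.** On day d the effect is d/7 of its final size. Its mean over days 1–7 is 28/49 = 4/7, so the simple average keeps (4/7)² = 16/49 of the gain in step 3. A model matched to this shape gains 2[20/7 − 16ρ/(1 + 7ρ)] over the two-day change.

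| ρ | Simple average, (16/49) × A/B | Shape-matched model |
|---|---|---|
| 0.3 | 1.5 | 2.6 |
| 0.5 | 1.0 | 2.2 |
| 0.7 | 0.8 | 1.9 |
| 0.9 | 0.6 | 1.8 |

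**5. The last-day contrast in a fitted model.** If day enters as a category, the last-day contrast with complete data gains only through the Day 0 adjustment: A/C = 2/(1 + ρ) = 1.54, 1.33, 1.18, 1.05. If dose-by-day is a straight line with a free dose term, its variance is B + 9(1 − ρ)/28 (day 7 lies 3 days from the mean day, and the squared deviations of days 1–7 sum to 28). That gives 0.535, 0.482, 0.349, 0.136 and gains of 2.6, 2.1, 1.7, 1.5.

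**6. Sensitivity.** With correlation decaying by day (AR(1)) and a constant effect, the adjusted mean gains 8.4 times at ρ = 0.3 and 3.0 times at 0.9 over the two-day change.

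**The case against.** The strongest reply is that section 9.0 does name linear models and repeated measures ANOVA, and the daily urine is their natural target. This has force. A reader might infer that the plan has decided only to graph the daily values, and the documents do not support that. They leave the general list and the specific rule unreconciled. But the sentence that deals with these data says graphs, so the ambiguity has to be resolved in writing. Classical repeated measures ANOVA would also drop any infant with a missed day. If 5% of samples were missed independently (an assumption), 0.95⁸ = 0.66, or about 28 of 42 infants, would be complete. The plan does not say that this form is intended.

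Two other strong readings also fail.

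- **That raw concentrations will be tested.** The text says levels and is silent on correction. Creatinine is assayed with no other stated use, so correction may well be intended. The gap is that it is not specified.
- **That most of the NO evidence is thrown away.** This is true of samples (6 of 8) but not always of information, because repeats are correlated. Under a constant effect the two-day change forgoes 1 − B/A = 78%, 68%, 58% and 48% at ρ = 0.3, 0.5, 0.7 and 0.9. The data are also still collected and shown.

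It can fairly be added that this is a pilot, that an end-of-treatment test with a descriptive trend is a defensible design, and that averaging over days can lose information if the effect builds slowly. Step 4 confirms the last point, so the averaged contrast should not be the sole summary. The pilot setting lowers the stakes, but it does not excuse an undefined primary variable.

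**Conclusion.** The point holds as a gap in specification with a real efficiency cost. A primary variable sampled about eight times per infant has assigned tests at two days only, the listed longitudinal methods are attached to nothing, and neither the NO measure nor the role of creatinine is defined.

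Under compound symmetry and ρ of 0.3 to 0.9, using all days with Day 0 adjustment gives about 4.5 to 1.9 times the information of the two-day change when the effect is constant. When it grows linearly, a shape-matched model gives about 2.6 to 1.8 times. A simple average then gains 1.5 times at ρ = 0.3, nothing at 0.5, and loses at 0.7 and above.

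The correlation, its structure and the effect shapes are assumptions. A reader might want to turn these ratios into power by starting from 0.80. The documents do not support that, because 0.80 was set for plasma citrulline. The cost of unadjusted urine dilution cannot be sized either, as no dilution variance is given.

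**What to change.** In section 9.0:

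1. Define the NO variable as log (nitrite + nitrate)/creatinine.
2. Assign it a linear mixed model on all post-dose days, with Day 0 value, dose, day and dose-by-day as fixed effects and a random infant effect. State whether day is a category or a linear trend, since step 5 shows that this decides how much the last-day contrast gains.
3. Prespecify the last-day (end-of-treatment) dose contrast, and report the contrast averaged over post-dose days beside it.
4. Keep the line graphs as display, and say which variables, if any, the listed repeated measures ANOVA is for.
5. Reconcile the day labels in section 5.0, so that the last-day sample is identified. Also reconcile the noon ± 2 hours urine window, described as between doses, with the 1200 ± 30 minutes dose time.

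The cost is wording and slightly more analysis work, plus reliance on a model for the within-infant correlation. No new samples or assays are needed.

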### 10.0 Ethics and the Protection of Human Subjects

The investigator will ensure that this study is conducted in full conformity with the principles set forth in The Belmont Report: Ethical Principles and Guidelines for the Protection of Human Subjects of Research of the US National Commission for the Protection of Human Subjects of Biomedical and Behavioral Research (April 18, 1979) and codified in 45 CFR Part 46 and/or the ICH E6; 62 Federal Regulations 25691 (1997).

The investigator must provide for the review and approval of this protocol and the associated informed consent/parental assent documents and recruitment material by an appropriate independent ethics committee (IEC) or IRB registered with the OHRP. Any amendments to the protocol or consent materials must also be approved before they are placed into use. In the United States and in other countries, only institutions holding a current US Federalwide Assurance issued by OHRP may participate.

Informed consent is a process that is initiated prior to the individual's (in this case, the legal guardians) agreeing to participate in the study and continuing throughout the individual's study participation. Extensive discussion of risks and possible benefits of this therapy will be provided to the parents/legal guardians of the study subjects. Assent forms describing in detail the study interventions/products, study procedures, and risks are given to the subject and written documentation of informed consent is required prior to starting intervention/administering study product. Assent forms will be IRB-approved and the parents will be asked to read and review the document. Upon reviewing the document, the investigator will explain the research study to the parents and answer any questions that may arise. The parents will sign the informed assent document prior to any procedures being done specifically for the study. The parents should have the opportunity to discuss the study with their surrogates or think about it prior to agreeing to participate. The parents may withdraw consent at any time throughout the course of the trial. A copy of the informed consent document will be given to the subjects for their records. The rights and welfare of the subjects will be

protected by emphasizing to the parents that the quality of their medical care will not be adversely affected if they decline to participate in this study.

## **Privacy/Confidentiality Issues**

Subject confidentiality is strictly held in trust by the participating investigators, their staff, and the sponsor(s) and their agents. This confidentiality is extended to cover testing of biological samples and genetic tests in addition to the clinical information relating to participating subjects.

The study protocol, documentation, data, and all other information generated will be held in strict confidence. No information concerning the study or the data will be released to any unauthorized third party without prior written approval of the Principal investigator.

Individuals authorized to view study records will be identified to the study subject on the informed consent but may include a study monitor or other authorized representatives of the sponsor or funding agency or federal or local agencies that regulate research including representatives from the Food and Drug Administration, Office of Human Research Protections, or the Institutional Review Board. Study records may also be made available for internal compliance reviews and quality assurance representatives.

These individuals may inspect all documents and records required to be maintained by the investigator, including but not limited to, medical records (office, clinic, or hospital) and pharmacy records for the subjects in this study. The clinical study site will permit access to such records.

In accordance with the Food and Drug Administration Amendment Act of 2007 (FDAAA) and The International Committee of Medical Journal Editors (ICMJE) member journals trials-registration policy as a condition for publication, this study will be registered in the public trials registry ClinicalTrials.gov, which is sponsored by the National Library of Medicine. Results will be published to clinicalTrial.gov when available but will not identify individual subjects.

# 11.0 Record Retention

The expected duration of this study is 1 year,

Since this research study accesses protected health information (PHI) and is covered under the Health Insurance Portability Accountability Act (HIPAA), consent forms that

include the HIPAA Authorization are to be retained for a minimum of 6 years from the date of the authorization.

Since this Research involves pediatric subjects, records shall be maintained until the last participating subject reaches age 21 or 10 years after completion of the research, whichever is later.

Research records will be maintained in accordance with the current version of the Texas Health Records Table 17-III Record Retention Schedule, Human Subject Research Records and Documents.

